3.3 OUTCOME MEASURES

3.3.1 Primary Outcome Measure

The primary endpoint is the proportion of relapse-free patients at month 12 after switching from NTZ to OCR.

Relapse is defined as:

Protocol: Ocrelizumab Providence Health & Services

Page 5 of 34 ML39655

- Occurrence of new or worsening neurological symptoms attributable to MS
- Symptoms persisting for > 24 hours
- Symptoms not attributable to confounding clinical factors (e.g., fever, infection, injury, adverse reaction to medication)
- Symptoms immediately preceded by a stable or improving neurological state for at least 30 days
- Symptoms accompanied by objective neurological worsening consistent with an increase of at least half a step on the EDSS scale, or 2 points on one of the appropriate FSS, or 1 point on 2 or more of the appropriate FSS; the change has to affect the selected FSS (i.e. pyramidal, ambulation, cerebellar, brainstem, sensory, or visual)

3.3.2 Secondary Outcome Measures

- Proportion of relapse free patients at months 3, 6, and 9
- Annualized Relapse Rate (ARR)
- Mean time to first relapse on OCR
- Proportion of patients free from MRI evidence of MS disease activity at months 3, 6, and 12
- Proportion of patients with new or enlarging T2 lesions at 3, 6, and 12 months. For patients with new or enlarging lesions, the number of new and enlarging lesions
- Proportion of patients with new Gd+ lesions at months 3, 6, and 12. For patients with new Gd+ lesions, number of new Gd+ lesions detected at months 3, 6, and 12.
- Change in the EDSS score from baseline to month 12.
- Change in MSIS-29 from baseline to months 6 and 12
- Number and type of AEs and SAEs
- Proportion of patients that discontinued OCR

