1. INTRODUCTION

Natalizumab (NTZ) is an extremely effective medication in reducing relapses and delaying or reducing sustained disability worseningⁱ. Therefore, NTZ is frequently prescribed in relapsing multiple sclerosis (MS) patients with highly active disease who have failed previous disease modifying therapy (DMT). However, there is increased risk of developing progressive multifocal leukoencephalopathy (PML) in patients infected with John Cunningham virus (JCV) who are being treated with NTZⁱⁱ. Unfortunately, the prevalence of antibodies to the JCV is relatively high, greater than 50 percent of the populationⁱⁱⁱ. The risk of developing PML reduces NTZ use, particularly after 2 years of NTZ exposure when the risk of PML increases^{iv}. Currently, the risk of developing PML is 4.22 per 1000^v. Therefore, NTZ is frequently stopped once a patient demonstrates evidence of JCV exposure by the presence of anti-JCV antibodies. However, the risk of disease progression has been reported to be higher when switching to another disease modifying therapy. In a study of 88 patients who had been treated on NTZ for 2 years were either maintained on NTZ, switched to another DMT, or remained off DMT. The relapse rate was 3.7% in the NTZ group versus 17.8% in the group on another DMT^{vi}. In another trial evaluating transitioning patients to dimethyl fumarate, the risk of relapse was 19.6% at one year.^{vii} Most recently, a multi-center trial was conducted in Sweden evaluating patients switching to rituximab or fingolimod after treatment with NTZ for greater than 6 months. Within 18 months of stopping NTZ, the relapse rate was 17.6% for fingolimod and only 1.8% for rituximab^{viii}.

In addition, there is no consensus on when to restart another disease modifying therapy although evidence suggests beginning treatment within 3 months of the last dose of NTZ^{ix}. Unfortunately, several studies have indicated that approximately a third of patients, within 3-6 months after withdrawal from NTZ, experienced a clinical and/or radiographic relapse^x.

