2. OBJECTIVES

2.1 PRIMARY OBJECTIVES

The primary objective of this study is to assess the efficacy of OCR in RMS patients who have been previously treated with NTZ by evaluating relapse rate, progression on MRI and disability progression.

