4.1.2 Inclusion Criteria

1. Male or female with relapsing form of MS, age 18 to 65, inclusive, at the time of informed consent.
2. In the opinion of the investigator, able to understand the purpose, risks, and responsibilities of the study and provide signed informed consent document.
3. Must have received a stable dose of NTZ for 12 or more consecutive months, and have had no evidence of on-NTZ disease activity (clinically or on MRI) for the 6 months prior to the screening visit.
4. Naïve to OCR.
5. No evidence, in the opinion of the investigators of significant cognitive limitation or psychiatric disorder that would interfere with the conduct of the study.
6. EDSS of ≤ 6.0 at screening.
7. Female patients of childbearing potential must practice effective contraception and continue contraception during the study.

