4.9.3 Efficacy Analysis

a. Primary Endpoint

Proportion of patients relapse free at 12 months after switching from NTZ to OCR

b. Secondary Endpoints

- Proportion of patients relapse-free at 3, 6, and 9 months after switching to OCR
- Mean time to first relapse
- MRI evidence of MS disease activity
- Proportion of patients with New or Enlarging T2 lesions at 3, 6, and 12 months. For patients with New or Enlarging T2 lesions, number of New and Enlarging T2 lesions.
- Proportion of patients with New Gd+ lesions detected at months 3, 6, and 12. For patients with New Gd+ lesions, number of New Gd+ lesions
- Annualized relapse rate (ARR)
- Change in EDSS from baseline to 12 months
- Change in MSIS-29 from baseline to 6 and 12 months

All patients that followed protocol will be used to evaluate the proportion of patients relapse-free at 3, 6, 9, and 12 months, mean time to first relapse, and ARR. This includes those that discontinued early but followed protocol up to discontinuation. All patients that followed protocol and did not discontinue will be used to evaluate MRI

evidence of MS disease activity at 3, 6, and 12 months, the change in MSIS-29 from baseline to 6 and 12 months, and the change in EDSS from baseline to 12 months.

A full analysis set consistent with the intent-to-treat (ITT) principle will also be used to analyze the proportion of patients relapse-free at 3, 6, 9, and 12 months, mean time to first relapse, and ARR using all subjects. Subjects who entered the trial and did not meet inclusion criteria may be excluded.

Summary statistics will be presented for continuous variables (mean, standard deviation, median, range) and categorical variables (counts and percentages). All analyses will use two-sided confidence intervals and p-values at the 0.05 significance level.

Primary Analysis

Kaplan-Meier survival analysis methodology will be used to determine the proportion of patients relapse-free at months 3, 6, 9, and 12. Median and mean time to first relapse with confidence intervals will be reported. Log rank tests and graphical presentations of Kaplan Meier curves with confidence intervals will be used to examine effects of center, gender, categorized age, categorized EDSS and duration of disease on survival distribution.

Secondary Analysis

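### MRI activity is reported by visit, with no reference scan and no definition through month 12, so the share of patients free of MRI activity all year cannot be derived

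*Combined protocol and SAP*

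**What the plan says.** Section 2.1 sets the primary objective as judging OCR "by evaluating relapse rate, progression on MRI and disability progression". MRI then appears only among the secondary outcomes in 3.3.2, in three forms:

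- the overall outcome, "Proportion of patients free from MRI evidence of MS disease activity at months 3, 6, and 12"
- for T2 lesions, the share of patients in whom any are new or enlarging at each of the same three visits, with lesion numbers for affected patients
- for enhancing lesions, "Proportion of patients with new Gd+ lesions at months 3, 6, and 12", likewise with lesion numbers

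The endpoint list in 4.9.3 shortens the first of these to "MRI evidence of MS disease activity" and does not define it. The Secondary Analysis paragraph of 4.9.3 plans only to summarise lesion counts by time point. It includes month 9, although sections 3.1 and 4.5.1 and Appendix A schedule MRI at screening and months 3, 6 and 12 only.

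Nowhere is a comparison scan named for new or enlarging lesions. No outcome is defined as absence of activity on any scan from the start of OCR to month 12.

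Relapse is handled differently: 4.9.3 estimates the relapse-free proportion by Kaplan-Meier, which is cumulative by construction. Section 4.9.3 also limits the MRI evaluation to patients who followed the protocol and did not discontinue, whereas the relapse analysis keeps early discontinuers up to the time they stop.

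**The concern.** The trial asks whether disease control on NTZ survives a switch to OCR. Patients enter only if they "have had no evidence of on-NTZ disease activity (clinically or on MRI) for the 6 months prior to the screening visit". The Introduction describes the failure to look for: "approximately a third of patients, within 3-6 months after withdrawal from NTZ, experienced a clinical and/or radiographic relapse". The direct MRI answer is therefore the share of patients with no activity on any scan over the year, and the plan does not define it.

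Two things follow. The three visit-specific proportions do not show how far the patients with activity at one visit are the same as those at another, so the year-long share cannot be recovered from them. And because the wording leaves the reading of *at* and the reference scan open, the 12-month MRI result could be settled after the data are seen, in an open-label single-arm study. A month 12 figure quoted alone could then look better than the year as a whole.

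**Working it through.** **1. The plan's own figures.** The documents give no MRI rate and no MRI sample size. The stated 45 patients (50 with attrition, section 4.9.6) concern relapse. They reproduce approximately with a two-sided Wald interval: 1.96² × 0.80 × 0.20 / (0.80 − 0.68)² = 42.7, so 43. At n = 45 the lower limit is 0.683, and 45 / 0.90 = 50. Nothing below depends on this.

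**2. Timing.** Inputs: activity 3 to 6 months after NTZ (Introduction), taken as 91 to 182 days; OCR started 4 to 6 weeks, or 28 to 42 days, after the last NTZ dose (3.1); visit days from 4.5.1.

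- Window on the OCR clock: 91 − 42 = Day 49 to 182 − 28 = Day 154.
- Month 3 scan: Day 84 ± 14, or Day 70 to 98, inside the window.
- Month 6 scan: Day 168 ± 14, or Day 154 to 182, at or just after its end.
- Month 12 scan: nominal Day 336, which is 336 + 28 = 364 to 336 + 42 = 378 days after the last NTZ dose, well after the window.

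So the first two scans are well placed to show early activity. The third, taken alone, is not.

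**3. What the three proportions determine.** Let a₃, a₆ and a₁₂ be the shares with activity on each scan, in the same patients. The share free on all three lies between 1 − (a₃ + a₆ + a₁₂), when no patient is active twice, and 1 − max(a₃, a₆, a₁₂), when the groups are nested. For illustrative per-visit rates of 90%, 94% and 96% free:

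- lower bound: 1 − (0.10 + 0.06 + 0.04) = 0.80
- upper bound: 1 − 0.10 = 0.90

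In 50 patients that is 40 to 45 people.

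**4. Sensitivity.** Same formula, other assumed per-scan activity rates:

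| Active at months 3 / 6 / 12 | Free at month 12 alone | Free on all three scans |
|---|---|---|
| 5% / 2% / 2% | 98% | 91% to 95% |
| 10% / 4% / 2% | 98% | 84% to 90% |
| 20% / 5% / 2% | 98% | 73% to 80% |
| 30% / 10% / 5% | 95% | 55% to 70% |

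**5. A patient with a new Gd+ lesion at month 3 and a quiet scan at month 12.**

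| Outcome at month 12, scored by visit | Counted as |
|---|---|
| Gd+ | Free, whichever reference scan is used |
| T2, read against the previous scan | Free |
| T2, read against the pre-OCR scan | Not free, if the lesion has left a visible new T2 lesion |

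For the combined MRI-free outcome, the unnamed reference scan therefore decides the answer.

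**6. Precision of a year-long figure.** With 45 patients, Wilson 95% intervals are 76.5% to 95.2% for 40 free (88.9%) and 66.2% to 89.1% for 36 free (80%).

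**The case against.** The strongest reply is that this is a question of wording. Section 3.3.2 uses the same construction for relapse at months 3, 6 and 9, which is analysed cumulatively. The MRI line could likewise mean free through each visit, and no sentence says otherwise. That is correct: a reader might infer that the plan prescribes non-cumulative scoring, but it only leaves the point open. The visit-based lesion summaries in 4.9.3 make the per-visit reading the natural one without making it a rule.

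A reader might also infer that early rebound goes undetected or that the MRI part of the objective is unanswered. The documents do not support either. Months 3 and 6 have their own MRI-free, T2 and Gd+ proportions and lesion counts, and month 12 is not named as the main MRI result. Nor do MRI and relapse cover different periods: scans read against the previous one run without a gap to month 12, and scans read against the pre-OCR scan span the same time.

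It is tempting to apply the cited third directly and set 100% free at month 12 against 67% free throughout. That figure mixes clinical and radiographic events after NTZ withdrawal. Using it here would treat all of it as radiographic, all of it as quiet by month 12, and the OCR start at 4 to 6 weeks as without effect, although section 3.2 expects a shorter washout to reduce recurrence.

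Finally, an entry criterion covering both relapse and MRI does not oblige the trial to have a combined outcome, since section 2.1 lists the components separately.

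None of this supplies the missing quantity. Whichever reading was meant, the definition and the reference scan still have to be written down.

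**Conclusion.** The point holds as an omitted definition that should be corrected. The primary endpoint and the sample size are unaffected. The plan shows when MRI activity occurs but does not prespecify how many patients had none all year, and that number cannot be worked out from what it does report.

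The size is illustrative because the documents give no MRI rates. At 90%, 94% and 96% free by visit, the year-long share is uncertain by 10 percentage points (80% to 90%). Across the assumed scenarios, a month 12 figure read alone exceeds the year-long share by 3 to 7 points when 5% are active at month 3, and by 18 to 25 points when 20% are. These gaps assume per-visit scoring and the same patients at every scan. They shrink if T2 is read against the pre-OCR scan and month 3 lesions stay visible. Sampling error at this trial's size is wider still, but it is unavoidable, whereas the missing overlap between visits is not.

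The restriction to patients who did not discontinue adds to the problem: someone with activity at month 3 who then stops could leave the MRI analysis altogether.

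**What to change.** In 3.3.2 and 4.9.3:

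1. Define MRI activity and name the pre-OCR (screening) scan as the reference for new or enlarging T2 lesions. That scan may be up to six weeks before Day 0, so state that lesions arising between it and Day 0 will count.
2. Add a secondary endpoint: the proportion of patients with no new Gd+ lesion and no new or enlarging T2 lesion on any post-baseline scan through month 12, with its 95% interval. Say whether unscheduled scans count.
3. Count patients with activity on any scan before discontinuation as not free, instead of removing them. Section 3.1 lets patients who stop OCR continue with study visits, so later scans may exist. The premature termination visit includes no MRI, so others will have scans missing.
4. State a missing-scan rule for patients with no activity seen but an incomplete series.
5. Keep the per-visit proportions and lesion counts as descriptive results, and reconcile the month 9 lesion count with the MRI schedule.

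An outcome combining freedom from relapse and from MRI activity would match the entry criterion, but it is optional.

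The cost is some wording and one more table from scans already scheduled, with no change to the sample size. The drawback for the sponsor is that, in the same patients, the year-long figure can only equal or fall below each per-visit figure.

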3.3.3 Ancillary Safety Outcome Measures

- Number and type of infusion related reactions based on dose including the severity of the reactions
- Number of and type of infections during the trial.

3.4 SAFETY PLAN

Patients will be evaluated at each study visit for the duration of their participation in the study (see Section 4.5 and Appendix A, Study Flowchart).

Protocol: Ocrelizumab Providence Health & Services

Page 6 of 34 ML39655

A full neurologic examination will be conducted at every visit (may be historical at screening if an exam was completed within 28 days prior to consent, and may be waived at baseline if screening and baseline are 7 or less days apart). Any worsening or new abnormality (including laboratory results) that is determined by the investigator as clinically significant will be recorded as an AE and will be monitored until resolution or stabilization. MS related symptoms are not to be reported as AEs unless, in the opinion of the investigator, the symptoms are unusually serious and relevant.

The recommendation from the OCR prescribing information dated 11/2018 is to pre-medicate with 100mg of methylprednisolone (or an equivalent corticosteroid) administered intravenously approximately 30 minutes prior to each OCR infusion to reduce the frequency and severity of infusion related reactions (IRRs) [see Warnings and Precautions (5.1) in prescribing information]. Also, it is recommended to pre-medicate with an antihistamine (e.g., diphenhydramine) approximately 30-60 minutes prior to each OCR infusion to further reduce the frequency and severity of infusion reactions.

Recommended medications to be available if there is an infusion reaction (per treating investigator discretion):

- A. Epinephrine – anaphylaxis
- B. Albuterol – bronchospasm or hypoxia
- C. Famotidine 20mg IV – hives, itching, or anaphylaxis
- D. Oxygen therapy – shortness of breath, chest pain, or hypoxia
- E. Acetaminophen – pain, fever, and headaches
- F. Methylprednisolone – hives, itching, shortness of breath, or anaphylaxis

Patients administered a sedating antihistamine for the treatment or prevention of IRRs should be given appropriate warnings concerning drowsiness and potential impairment of ability to drive or operate machinery.

Pre-medications, infusion reaction management, and infusion reaction medications are to be left to treating investigator discretion.

Suggested Management of IRRs

Severe IRRs

If a patient experiences a severe IRR or a complex of flushing, fever, and throat pain symptoms, the infusion should be interrupted immediately and the patient should receive symptomatic treatment. The infusion should be re-started only after all symptoms have resolved. The initial infusion rate at restart should be half of the infusion rate at the time of onset of the reaction.

Mild-Moderate IRRs

If the event that a patient experiences is a mild to moderate IRR (e.g. headache), the infusion rate should be reduced to half the rate at the time of the event. This reduced rate should be maintained for at least 30 minutes. If tolerated, the infusion rate may then be increased according to the patient's initial infusion schedule.

See Section 5 (Assessment of Safety) for complete details of the safety evaluation for this study.

3.5 COMPLIANCE WITH LAWS AND REGULATIONS

This study will be conducted in accordance with current ICH GCP Guidelines and the Code of Federal Regulations for clinical research. Any amendment to the study protocol must be approved by Providence IRB and the IRB or Ethics Committee of each site before implementation. AEs and protocol deviations must be reported according to the guideline of the IRB or Ethics Committee of each study site.

4.0 MATERIALS AND METHODS

4.1 SUBJECTS

4.1.1 Subject Selection

Subject selection will be based on meeting all of the required inclusion and exclusion criteria to be eligible to participate in the trial. Subjects are eligible to participate regardless of their JCV status.

4.1.2 Inclusion Criteria

1. Male or female with relapsing form of MS, age 18 to 65, inclusive, at the time of informed consent.
2. In the opinion of the investigator, able to understand the purpose, risks, and responsibilities of the study and provide signed informed consent document.
3. Must have received a stable dose of NTZ for 12 or more consecutive months, and have had no evidence of on-NTZ disease activity (clinically or on MRI) for the 6 months prior to the screening visit.
4. Naïve to OCR.
5. No evidence, in the opinion of the investigators of significant cognitive limitation or psychiatric disorder that would interfere with the conduct of the study.
6. EDSS of ≤ 6.0 at screening.
7. Female patients of childbearing potential must practice effective contraception and continue contraception during the study.

4.1.3 Exclusion Criteria

1. History of primary or secondary progressive multiple sclerosis.
2. Evidence of active hepatitis B infection at screening.
3. Any mental condition of such that patient is unable to understand the nature, scope, and possible consequences of the study.
4. Patients with untreated hepatitis C or tuberculosis. Patients who have history of PML or known to be HIV positive, per standard care.
5. Any persistent or severe infection.
6. Pregnancy or lactation.

7. Significant, uncontrolled somatic disease or severe depression in the last year.
8. Inability to complete an MRI.
9. Previous treatment with B-cell targeted therapies.
10. Current use of immunosuppressive medication.
11. Patients who have had evidence of disease activity within the 6 months prior to screening. This includes MS relapse, or new or enlarging T2 lesions or Gd+ enhancing lesions, or disability progression.
12. Patients with any significant comorbidity that in the opinion of the investigator, would interfere with participation in the study.

4.2 METHOD OF TREATMENT ASSIGNMENT

This is an observational study in patients who will receive OCR as part of their standard care.

4.3. STUDY TREATMENT

Patients will be initiated on OCR after informed consent and screening assessment have been completed. The first dose of OCR will be administered between 4 and 6 weeks after the last dose of NTZ. OCR will be prescribed by patient's neurologist as standard of care and paid for by the patient/patient's insurance.

4.3.1 Dosage, Preparation, Administration and Storage

Ocrelizumab Formulation Packaging, and Handling

The following requirements are listed in the OCR prescribing information dated 11/2018 and are to be followed as part of the standard of care preparation of OCR for infusion. The study team is not responsible for collecting or reviewing data on how the drug was packaged, prepared, handled, or stored for the purposes of this trial.

Ocrelizumab will be supplied by the commercial pharmacy in a liquid formulation containing 30-mg/mL ocrelizumab in 20mM sodium acetate at pH 5.3, with 4% trehalose dihydrate and 0.02% polysorbate 20. The drug product is provided as a single-use liquid formulation in a 15-cc, type I USP, glass vial fitted with a 20-mm, fluoro-resin, laminated stopper and an aluminum seal with a flip-off plastic cap and contains a nominal 300 mg ocrelizumab. No preservative is used as each vial is designed for single use.

The ocrelizumab drug product must be diluted before administration. Solutions of ocrelizumab for IV administration are prepared by dilution of the drug product into an infusion bag containing 0.9% sodium chloride to a final drug concentration of 1 to 2 mg/mL.

Ocrelizumab may contain fine translucent and/or reflective particles associated with enhanced opalescence. Do not use the solution if discolored or if the solution contains discrete foreign particulate matter.

The infusion solution must be administered using an infusion set with an in-line, sterile, non-pyrogenic, low-protein-binding filter (pore size of up to 0.2 micrometer).

The prepared infusion solution of ocrelizumab is physically and chemically stable for 24 hours at 2–8°C and subsequently 8 hours at room temperature. The prepared infusion solution should be used immediately. If not used immediately, it can be stored up to 24 hours at 2–8°C. Infusion solution must be completely administered to the patient within 32 hours of preparation (not exceeding 24 hours at 2–8°C and 8 hours at room temperature). In the event an IV infusion cannot be completed the same day, the remaining solution should be discarded.

Dosage, Administration, and Compliance

Ocrelizumab 300mg IV will be given on Day 0 and repeated with the same dose on Day 14±2. Patients will then receive ocrelizumab 600mg IV every 24 weeks. Medication will not be provided by the study.

Although ocrelizumab may be administered on an outpatient basis, patients may be hospitalized for observation at the discretion of the investigator. Ocrelizumab infusions should always be administered in a hospital or clinic environment under close supervision of the investigator or a medically qualified staff member.

See section 3.4 for recommended pre-medications and recommended medications to treat IRRs. For the 300-mg dose, each ocrelizumab infusion should be given as an IV infusion over approximately 150 minutes (2.5 hours). For the 600-mg dose, each ocrelizumab infusion should be given as an IV infusion over approximately 215 minutes (3.5 hours). Since transient hypotension may occur during ocrelizumab infusion, the investigator may wish to withhold anti-hypertensive medications 12 hours prior to ocrelizumab infusion.

Ocrelizumab must not be administered as an IV push or bolus. Well-adjusted infusion pumps should be used to control the infusion rate, and ocrelizumab should be infused through a dedicated line. It is important not to use evacuated glass containers (to prepare the infusion), which require vented administration sets, because this causes foaming as air bubbles pass through the solution.

After completion of the infusion, the IV cannula should remain in situ for at least 1 hour to allow for administration of drugs intravenously, if necessary, in the event of a delayed reaction. If no adverse events occur during this period of time, the IV cannula may be removed and the patient may be discharged.

See the OCR prescribing information dated 11/2018 for detailed instructions on drug preparation, storage, and administration.

